### 4.2 Scientific Rationale for Study Design

Prior randomized controlled clinical trials have already established efficacy of this intervention approach. Our aim is not to examine efficacy of pain self-management, but rather to identify the role of sleep deficiency on self-management behaviors, and our pre-post design maximizes power to accomplish this.

### 4.3 Justification for Intervention

CBT is a well-established intervention for management of acute and chronic pain in adolescents and has been effectively delivered using digital technologies to improve access to evidence-based care (2). We have had tremendous success in our research studies reaching youth with chronic pain using internet and smartphone technologies, including those in rural areas and with health disparities who do not have access to specialist services (54, 72, 73, 75). CBT interventions are flexible and can be delivered in brief treatment protocols. Our WebMAP intervention teaches six different cognitive and behavioral skills focused on

### 4.4 End-of-Study Definition

Once the final enrolled participant (target: 80) has completed their 6 month follow-up assessment (T4), all data collection for the study will be complete.

## 5 STUDY POPULATION

### 5.1 Inclusion Criteria

(a) age 12 to 17 years, (b) diagnosed by the attending pain physician with a primary pain disorder involving abdominal, headache, or musculoskeletal pain, (c) pain duration > 3 months, (d) average rating  $\geq 5$  on two items from the Brief Pain Inventory asking about average pain intensity and activity interference in the past week (0-10 scale), and (e) has access to the Internet. Youth on a stable dose (x 2 months) of medications (antidepressants, anticonvulsants, etc) for pain or sleep will be eligible.

### 5.2 Exclusion Criteria

(a) diagnosis of a comorbid serious health condition (e.g., cancer), (b) parent or adolescent does not speak English, (c) has active psychosis or suicidal ideation, (d) is currently taking stimulating medications, and (e) has a diagnosed primary sleep disorder (e.g., sleep apnea, narcolepsy).

### 5.3 Lifestyle Considerations

N/A

### 5.4 Screen Failures

Screen failures are defined as participants who consent to participate in this study but are not subsequently assigned to the study intervention or entered in the study. Individuals who do not meet the criteria for participation in this trial (screen failure) because of meeting one or more exclusion criteria that are likely to change over time may be rescreened. Examples include terminating use of stimulating medications. Rescreened participants will be assigned the same participant number as for the initial screening.

### 5.5 Strategies for Recruitment and Retention

1. Our target sample size includes 80 adolescents ages 12-17 of any sex, race and ethnicity. Based on the percentage of eligible participants in previous studies with similar criteria, we anticipate that we will need to screen 100 participants in order to reach our target sample size of 80 adolescents.

a. Regarding the NIH Policy and Guidelines on The Inclusion of Women and Minorities as Subjects in Clinical Research:

i. Our sample will include female children/adolescents and mothers or female caregivers. We anticipate a large proportion of child and caregiver participants to be female – in previous studies with a similar population, 74% of child participants and 90% of parent participants were female.

ii. Our sample will include minorities. Specifically, we estimate enrolling participants at the following rate: 11.0% Hispanic/Latino and 89.0% not Hispanic/Latino. In terms of racial categories, we expect to enroll participants in the following proportions: 78.4% White, 7.0% Asian, 4.0% More than One Race, 9.0% Black or African American, 1.4% American Indian/Alaska Native, and 0.2% Native Hawaiian or Other Pacific Islander. Referrals will come from the Seattle Children's Pain Clinic.

iii. Participants will be recruited via referral from providers at Seattle Children's Pain Clinic and via EMR review. Health care providers will inform patients and families about the study and provide families with study information in the form of a flyer. Providers will then ask families if they are willing to be contacted by research staff to assess interest in the study and discuss participation. The provider will refer interested, potentially eligible participants by entering participant and parent names and contact information into a secure REDCap database hosted at SCH, or may send the referral by secure fax, email, or voicemail. Families who do not give permission for their information to be shared with SCH by the referral site may still contact SCH staff or submit their information to SCH via a secure link on the study website (self-referral), or via email or secure voicemail.

iv. Participants will be individually compensated after each completed study assessment. At each time point the child will have an opportunity to earn a \$40 Amazon gift card for completing that assessment. With four time points, the child can earn up to \$160 if all assessments are completed. Participants will not receive additional reimbursement for completing the intervention.

v. We will utilize standard procedures to maximize retention rates for this trial, incorporating the following elements:

- a. Creation and use of a detailed contact protocol to specify when participants should be contacted throughout different study phases
- b. Staff will build rapport with family – consistent contact with the same research coordinator(s)
- c. Open communication with family re: contact preferences (time, method)
- d. Use of varied contact methods according to family preference, study timeline, and past contact history (text, email, phone, app-based reminders and encouragement)
- i. Text and email communication (based on templates) from the study team will be used for the following types of situations: initial & follow-up recruitment messaging, consent call information and scheduling/rescheduling, missing survey question follow-up, survey completion reminders, diary survey completion reminders, gift card distribution, incomplete baseline surveys, website/app login instructions, website/app usage reminders, check-ins, and updates, discharge survey follow-up, and assessment start date scheduling
- e. Use of adequate incentives for survey and diary completion
- f. Frequent reminders for survey and diary completion; discussion with family of assessment timelines and start dates to ensure they work with family schedule

g. Frequent monitoring of program usage and reminders via app and text/email/call as needed to encourage program adherence  
(mobile app)

vi. Seattle Children's research staff will screen each completed survey for any items that were not filled out by the participant. Seattle Children's research staff will then follow up with the participant to recover information for missed questions unless the participant skipped that question intentionally.

## 6 STUDY INTERVENTION(S) OR EXPERIMENTAL MANIPULATION(S)

### 6.1 Study Intervention(s) or Experimental Manipulation(s) Description

All youth and parents will receive access to the WebMAP program, which consists of two separate, password-protected web programs, one for teens and one for parents completed in an 8 week period. The program design and treatment content of WebMAP follow cognitive-behavioral, social learning, and family systems frameworks. The eight adolescent modules include: 1) education about chronic pain, 2) recognizing stress and negative emotions, 3) deep breathing and relaxation, 4) implementing coping skills at school, 5) cognitive skills (e.g., reducing negative thoughts), 6) lifestyle interventions, 7) staying active (e.g., pleasant activity scheduling), and 8) relapse prevention. The eight parent modules are: 1) education about chronic pain, 2) recognizing stress and negative emotions, 3) operant strategies I (using attention and praise to increase positive coping), 4) operant strategies II (using rewards to increase positive coping and reach school goals), 5) modeling, 6) lifestyle, 7) communication, and 8) relapse prevention.

The program is designed to enhance pain self-efficacy, defined as perception of one's ability to successfully carry out daily activities while in pain, and to promote activity participation. Youth set structured and personalized goals aimed at improving their pain and functioning. Given the importance of homework and practice to behavior change, several components (e.g., positive feedback loops) actively encourage user attention and motivation in order to promote skills acquisition and rehearsal. Using a diary function on the web site, youth track their symptoms in real-time and can generate customized reports and graphs from their data. The web site uses a multimedia-rich format (e.g., animations, videos, audio clips) to deliver content. The website is built on a responsive platform and can be viewed on multiple devices (e.g., smartphones, laptops, tablets) to increase ease and flexibility of use. All website content is (a) written at a grade 5-6 reading level, (b) developmentally appropriate for the full age range of youth, and (c) is based on a unifying theme/narrative.

### 6.2 Measures to Minimize Bias: Randomization and Blinding

After baseline assessment is completed, participants will receive access to the study intervention. Research staff will set up accounts and instruct the participants regarding how to access the WebMAP intervention. There is no masking as this is not a randomized trial.

### 6.3 Study Intervention/Experimental Manipulation Adherence

Treatment is consistently delivered via the web programs. Study staff ensure that each participant has downloaded and set up the intervention program within 7 days of completing the baseline assessment. The web programs track each time a parent or youth uses the program and document when lessons are completed. The primary measure of adherence will be the number of modules completed.

#### 6.4 Concomitant Therapy

We will collect information from parents after each treatment phase on mental health services that may qualify as concomitant therapy. Parents report on if their teen received mental health services, if services were for pain management, if services were related to a pre-existing problem, and how many sessions their teen had.

## 7 STUDY INTERVENTION/EXPERIMENTAL MANIPULATION DISCONTINUATION AND PARTICIPANT DISCONTINUATION/WITHDRAWAL

### 7.1 Discontinuation of Study Intervention/Experimental Manipulation

Not applicable – this is a minimal risk, adjunctive educational intervention that provides cognitive and behavioral skills for pain management.

### 7.2 Participant Discontinuation/Withdrawal from the Study

Participants may withdraw from the study or intervention voluntarily at any time. Participants may be discontinued from the study per investigator discretion if they do not complete the baseline assessment, develop a new complex medical condition (e.g. new cancer diagnosis),.

### 7.3 Lost to Follow-Up

Seattle Children's research staff will attempt to collect data from enrolled participants who we are unable to reach or have not completed prior assessments. Staff will follow a detailed contact protocol to contact participants at regular intervals appropriate for their study timeline and utilize a variety of contact methods according to participant preference to maximize participant retention and engagement.

## 8 STUDY ASSESSMENTS AND PROCEDURES

### 8 STUDY ASSESSMENTS AND PROCEDURES/EVALUATIONS

#### 8.1 Study Procedures/Evaluations

Assessments will occur at baseline ( $T_1$ ), immediately after intervention (2 months;  $T_2$ ), and repeated at 6 months ( $T_3$ ). Mediators will be assessed at an additional mid-treatment (4 weeks) data point. The intervention phase will last 2 months (8 weeks). All questionnaires will be administered using Research Electronic Data Capture (REDCap), a secure web-based tracking and on-line data acquisition system (40). We have used this system successfully in multiple studies to date. Estimated time burden is 10 minutes for parents and 40 minutes for teens. Response burden is minimized by the online administration, which allows saving and storing of responses.

**Screening Measures.** Participants will complete the Pediatric Sleep Questionnaire (41) to screen for sleep-disordered breathing. If they screen positive they will be referred for clinical evaluation and will not be enrolled. Parents will complete a Demographic Questionnaire to assess sociodemographic variables and pain history.

**Mediators.** Positive and negative affect will be assessed with the Positive and Negative Affect Scale-Child version (PANAS-C; (48). The PANAS-C consists of two mood scales with 10-items each rated on a 5-point scale for assessing positive (e.g., inspired, strong) and negative affect (e.g., guilty, scared). Both scales are internally consistent, uncorrelated, and stable over a 2-month time period; good convergent and discriminant validity have also been demonstrated (48). Executive functioning will be assessed with the Behavior Rating Inventory of Executive Function (BRIEF-2) (49), a short 12-item well validated self-report measure that assesses executive function behaviors (e.g., inhibitory control, working memory, planning and organization) in home and school environments providing three indices of regulation, Behavioral, Emotional, and Cognitive.

**Sleep Measures.** We will conduct a rigorous and comprehensive assessment of sleep patterns and behaviors to assess disrupted sleep, amount of sleep, sleep quality, and insomnia symptoms. Adolescents will complete validated self-report questionnaire measures, 7 days of actigraphic monitoring, and a sleep diary. Actigraphic monitoring. Youth will complete 7-days of actigraphic monitoring at each time point with the Actiwatch-2 (AW2; Phillips Respironics, MiniMitter Company Inc., Bend, OR). We will mail an Actiwatch to each participant's home (along with written instructions) using the same procedures that we successfully applied in our prior projects. Averages will be computed across the 7-day periods. We will use three variables in our analyses: minutes of estimated sleep, wake time after sleep onset and sleep efficiency, providing estimates of the amount of sleep and disruption to sleep. Subjective measures. The short form of the Adolescent Sleep Wake Scale (ASWS) is a 10-item measure of sleep quality validated in adolescents with chronic pain and other medical conditions (42). A total score indicates overall perception of sleep quality. Youth will also complete the 7-item Insomnia Severity Index (43) to specifically measure severity of insomnia symptoms. *Although developed*

for adults, the ISI has shown strong validity and reliability estimates in adolescents in our own and other's published work, e.g., (44). Total scores above 8 on the ISI indicate risk for clinically significant insomnia. Diary ratings. A sleep diary will be administered to assist with actigraphy scoring, to provide information on sleep and wake times, and to collect daily sleep quality ratings. Youth will complete the diary at bedtime and upon waking. Each morning youth will rate global sleep quality on an 11-point NRS. We have used this method in prior studies achieving high compliance (over 85%) in completing a minimum of 5 of 7 days of diary entries.

**Self-management processes.** Using Common Data Elements for Self-Management, 3 self-management processes will be assessed. Pain self-efficacy. The Pain Self-Efficacy Scale (45) is a 7-item measure that assesses the child's beliefs in carrying out activities when in pain. The scale has demonstrated good internal consistency, cross-informant reliability with parent report, and strong construct validity. Patient activation. The Patient Activation Measure (46) is a 13-item questionnaire that assesses an individual's knowledge, skill and confidence for managing their health and health care. The PAM uses a 0-100 scale resulting in 4 levels of activation, from low (1) to high (4). The measure is not disease specific, and has been successfully used with a wide variety of chronic conditions. Although developed for adults, the PAM has been used in children ages 12 and above, is reliable, and shows strong construct validity. Self-management skills. The Transition Readiness Assessment Questionnaire 3.0 (47) is a 14-item measure that assesses self-management skills related to healthcare interactions, self-advocacy, and decision-making. The TRAQ has been validated in children 12-18 years with a broad range of health conditions, has good reliability and strong construct validity.

**Pain and Health Outcome Measures.** We will measure daytime function and health outcomes using well-validated instruments. WebMAP has diary assessments programmed into the web site to prospectively collect pain intensity and pain-related disability data over 7-day periods. Child pain intensity will be rated on the online diary using an 11-point NRS (50). The CALI is a validated instrument of pain-related disability measured by youth difficulty in performing usual daily physical, social, and recreational activities (e.g., going to school, running, walking) due to pain (51). We will measure fatigue using the PedsQL Multidimensional Fatigue Scale (52), which yields three scores for general fatigue, cognitive fatigue, and sleep-rest fatigue. It has been widely used in many pediatric chronic health conditions demonstrating strong reliability and validity. Global health will be assessed with the PROMIS pediatric global health measure (53), a 7-item measure summarizing a child's physical, mental, and social health into a single score. Concurrent validity has been recently demonstrated with lower scores for children with chronic conditions and strong relationships with measures of positive health.

**Treatment engagement, adherence, and acceptability.** Treatment engagement will be measured by completion of at least 1 module while adherence is defined as the completion of 6 or more modules. The administrative interface of the WebMAP program has a tracking system in place for recording each time a user logs onto the program. Each module contains multiple-choice quizzes concerning the content presented as well as behavioral assignments, fill-in-the-blank fields, and use of the diary tracker. Data fields completed within modules are stored, generating a comprehensive activity record of module specific use including self-management tasks. Treatment acceptability and satisfaction will be assessed with the Treatment Evaluation Inventory (54), which we have adapted for pain self-management, and ratings of global

impression of change.

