## 1.2 Schema

### *Study Flow*

## 1.3 Schedule of Activities

	Pre-Screening	Consent	Time 1	Time 2	Time 3	Time 4
EMR Review	X					
Eligibility						
Informed Consent		X				
Demographics			X			
Sleep assessment			X		X	X
Outcome evaluation			X		X	X
Mediator evaluation				X		
Intervention			X	X		
Adverse events reporting				X	X	X

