**We propose that sleep deficiency is a modifiable pathway that may influence success of pain self-management.** Sleep deficiency is associated with general deficits in higher-order and complex cognitive functions and reduced self-regulatory skills (e.g., 17), which may influence self-management tasks. As reviewed by Stickgold and Walker (2013), sleep (a) enhances cognitive flexibility in problem solving (19, 20), (b) assists in the integration of new learned information (21), and (c) is critical for promoting memory associations (22). Sleep also affects elements of self-control such as subjective effort, perceived exertion, and choice (23) and short sleep duration increases negative affect and decreases positive affect (24). *Because self-management relies on organization, memory, and behavioral activation, we hypothesize that positive and negative affect and executive function will mediate the relationship between sleep deficiency and self-management.* Relevant research in other pediatric chronic conditions has examined effects of sleep deficiency on self-management behaviors in youth. For example, in a study in youth with diabetes, greater sleep deficiency was related to reduced treatment adherence (25). Similarly, in youth receiving a physical activity self-management intervention, greater sleep deficiency was related to reduced efforts at self-monitoring, goal-setting, and social support behaviors (26). Thus, our scientific premise is that in addition to the direct effect of sleep on pain and functioning, sleep deficiency also decreases youth's acceptability of treatment, motivation to engage with treatment, and to implement self-management tasks and behaviors.

This scientific premise is supported by our own pilot data showing that several aspects of sleep deficiency are related to treatment acceptability and outcomes. Specifically, in pilot work we found that shorter sleep duration at baseline predicted reduced benefit (i.e., less improvement in pain-related disability) with a self-management intervention for chronic pain (27) and that poor baseline sleep quality was associated with lower youth perception of overall treatment acceptability. However, to date, studies have not determined the impact of sleep deficiency on pediatric pain self-management.

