### 9.3 Statistical Analyses

Data will be reviewed for completeness and errors including consistency checks for relevant variables. Tabular and graphical methods of data exploration including frequency tables, scatterplots, and box plots will be used to explore distributions of study variables. For the primary analytic plan, we will rely

on panel and latent growth models (LGM), within the structural equation modeling (SEM) framework (55-57). Both approaches can be implemented within a manifest and/or latent variable context (58). Unlike traditional repeated-measures analysis of variance, SEM allows for a more accurate and flexible approach to analyzing repeated measures data by simultaneously modeling change in the means (fixed effects) and in the variance and covariance of initial level and change (random effects) (56, 59-61). We include biological covariates of age, sex, and pain location in all models. We expect 10% attrition for a final projected sample size of  $n = 72$ . Full Information Maximum Likelihood (FIML) estimation will be used to handle missing data related to attrition and non-response (62) incorporating robust standard errors or bootstrapping to correct for non-normality (61). FIML estimation improves accuracy and power relative to other missing data handling methods (63, 64).

**Aim 1. Characterize the relationship between baseline sleep deficiency and self-management processes.** We will use structural equations (65, 66) to assess interrelations, direct effects, and indirect mediation effects in a longitudinal panel model. Mediation will be tested by decomposing a total effect of each sleep deficiency measure (duration, wake time, quality, insomnia symptoms) on self-management processes into direct effects and indirect effects (65, 66). Significance tests of indirect effects will be carried out using the Monte Carlo (*empirical-M*) method to obtain 90% asymmetric confidence intervals (67-69).

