Expected Results, Interpretation, and Possible Pitfalls. We expect the higher the level of sleep deficiency the higher negative affect, lower positive affect, *lower executive functioning*, lower the behavioral activation, self-efficacy, and self-regulation at baseline. There will likely be an indirect effect of sleep deficiency on affect *and executive function* and of affect *and executive function* on self-management processes. *We also expect that a significant indirect effect will indicate that sleep deficiency affects change in self-management processes by influencing affect or executive function.*

**Aim 2. Determine the effect of baseline sleep deficiency on treatment acceptability, engagement with, and benefit from an internet-delivered pain self-management intervention.** We will use LGMs to model individual differences in final acceptability and engagement status and the rates of change in global health, pain symptoms, fatigue, and pain-related disability (56, 59-61) and to test the proposed predictive and mediated effects.

Expected Results, Interpretation, and Possible Pitfalls. We expect that global health will improve over the course of the study while pain, fatigue, and pain-related disability will decrease. We also expect that participants will significantly vary around the average intercept and slope. We expect the higher the initial level of sleep deficiency the shallower the increase in global health over time and the shallower the decline in pain, fatigue, and pain-related disability. Across all models we expect less than 10% attrition over the course of the study based on our prior work (27). We will use the maximum likelihood estimation option in the Mplus 7.3 software program to deal with missing data and use the robust standard error option to correct for non-normality (61).

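### The schedule marks mediators at Time 2 only, while 8.1, 8.2 and 9.3 point to a baseline score, and 9.3 names no mediator wave for H2 or H5

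*Combined protocol and SAP*

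**What the plan says.** - **Schedule (1.3).** The row "Mediator evaluation" has one mark, under Time 2. Sleep and outcome assessments are marked at Times 1, 3 and 4.
- **Procedures (8.1, and 8.2 in the same words).** After a list of assessments that begins with baseline: "Mediators will be assessed at an additional mid-treatment (4 weeks) data point".
- **Visit labels.** Section 8.1 calls the 2-month visit T2 and the 6-month visit T3. Section 4.4 makes the 6-month visit T4, Section 3 places the outcomes at T1, T3 and T4, and 5.5 pays for four time points.
- **Expected results for Aim 1 (9.3).** The sentence opens "We expect the higher the level of sleep deficiency the higher negative affect, lower positive affect", goes on to executive functioning, and ends "lower the behavioral activation, self-efficacy, and self-regulation at baseline".
- **Mediation analysis (9.3).** H2 is tested through "indirect mediation effects in a longitudinal panel model". The stated interpretation is that "a significant indirect effect will indicate that sleep deficiency affects change in self-management processes by influencing affect or executive function". For Aim 2, growth models address "individual differences in final acceptability and engagement status and the rates of change in global health" and the other benefit measures, and also carry the mediated effects. No mediator wave is named for either hypothesis.

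**The concern.** H2 and H5 are the mechanism hypotheses of a study whose purpose is mechanism. There is one arm and sleep is observed, not assigned, so much of the weight of a mediation claim rests on the order of measurement.

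If mediators are first measured at week 4, two things follow. The baseline relation that 9.3 anticipates cannot be looked at. And an indirect effect through the week-4 score could reflect change in affect after baseline, or a sleep-affect relation that was there at entry and carried forward. Section 9.3 commits in advance to an interpretation in terms of change without saying which of these it means to estimate. A Time 1 score that was not collected cannot be recovered.

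Engagement adds a further difficulty. Logins, modules and assignments accumulate from the start of the program, so part of the outcome occurs before a week-4 mediator.

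**Working it through.** **1. Which visit is Time 2?** With the 6-month visit as T4 (4.4) and outcomes at T1, T3 and T4 (Section 3), T3 is post-treatment and T2 is mid-treatment. The schedule agrees: at Time 2 the intervention is still running and no outcome is evaluated. Section 8.1 is the exception. A reader who applied its labels to the schedule would move the mediator to the post-treatment visit.

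**2. Is a baseline mediator score planned?**

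| Place | What it implies |
|---|---|
| 1.3 | No: one mark, at Time 2 |
| 8.1, 8.2 | Probably: week 4 is additional to a list that starts with baseline |
| 9.3, expected results | Most naturally yes: the sentence on affect and executive functioning ends at baseline |
| 9.3, H2 and H5 models | Silent |

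**3. Module timing.** At one module per week for 8 weeks (1.1), 4/8 = 50% of modules are due by week 4. If weeks run from baseline and set-up takes up to 7 days (6.3), the count is 3 to 4. The engagement threshold of at least one module (8.1) would normally be met before week 4; the adherence threshold of six modules would not. Access to the program follows baseline (6.2), so a Time 1 mediator precedes all use.

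**4. What the missing baseline score does: an illustration.** Every path here is assumed; none comes from the documents. Let r be the correlation of sleep with affect at baseline, s the stability of affect from baseline to week 4, and b the path from week-4 affect to the outcome. Sleep has no effect on affect after baseline. The week-4 indirect effect without the Time 1 mediator is then r × s × b, and with it, zero. Take b = 0.35:

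- r = 0.2, s = 0.5: 0.2 × 0.5 × 0.35 = 0.035
- r = 0.5, s = 0.7: 0.5 × 0.7 × 0.35 = 0.1225

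Simulated at n = 72 (the projected final sample in 9.3) with the 90% Monte Carlo interval of 9.3, the baseline outcome in the model, a baseline outcome-affect link of 0.3, and 1,500 replicates:

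| r | s | Interval excludes zero, no T1 mediator | With T1 mediator |
|---|---|---|---|
| 0.2 | 0.5 | 25% | 11% |
| 0.2 | 0.7 | 34% | 9% |
| 0.35 | 0.5 | 45% | 10% |
| 0.35 | 0.7 | 60% | 7% |
| 0.5 | 0.5 | 68% | 8% |
| 0.5 | 0.7 | 90% | 10% |

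The result depends heavily on b. In a separate set (s = 0.65, r = 0.2 to 0.5, four covariates, no effect of week-4 affect on the outcome, no direct path from baseline affect), the unadjusted rate was only 1% to 6%.

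**5. What adjustment costs.** Also on assumed paths, with a true sleep effect on affect after baseline (sleep path 0.2 to 0.3, mediator-outcome path 0.3 to 0.5), adding the Time 1 mediator cut detection from 80%-99% to 43%-89%.

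**The case against.** **The table may be damaged.** The schedule was read from a PDF and its eligibility row carries no mark at all. This stands as a caution. A reader might infer from 1.3 that no baseline mediator will be collected; the documents do not establish that, and 8.1 reads more naturally the other way. Against pure loss, the mediator row is blank exactly where sleep and outcome are marked, which looks deliberate. Even if marks were lost, the labels in 8.1 and the silence of 9.3 on the mediator wave remain.

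**The 9.3 sentence is an expectation, not a listed test, and at baseline may attach only to its last items.** Fair in part, which is why the sentence most naturally requires a baseline score and does not strictly prove one.

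**The relation at entry may be the mechanism.** This stands. Section 2.2 says "short sleep duration increases negative affect and decreases positive affect", so sleep may already have acted through baseline affect. A reader might take the unadjusted rates above as false positives. They are false only if mediation is defined as change after baseline, and the plan does not define it so.

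**Engagement as hypothesised is total use.** This also stands. A reader might conclude that use in weeks 5 to 8 should replace it. That would change the outcome in H3 and H5 and lose any effect carried through early use. With a Time 1 mediator the overlap with the outcome disappears.

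**Conclusion.** The point holds and should be fixed; confidence is moderate. The schedule as printed conflicts with the natural reading of 8.1, 8.2 and 9.3 on whether mediators are measured at baseline, the labels in 8.1 conflict with 1.3, Section 3 and 4.4, and 9.3 leaves the mediator wave open for H2 and H5. What matters is conditional: if 1.3 is followed, the baseline relation cannot be examined and a week-4 indirect effect cannot be assigned to change after baseline.

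The firm sizes come from the documents: mediators at 1 of 4 time points, and about 4 of 8 modules before week 4. The simulated rates show only that the choice of model can matter a great deal or very little; they estimate nothing about this trial.

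The documents do not support a claim that the mediation analyses are invalid. If a Time 1 score is in fact collected, what remains is to correct the table and labels and to specify the models. Nor would better timing make any of these analyses causal: sleep is not assigned, so all are associational.

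**What to change.** 1. **Schedule and labels.** Mark mediator evaluation at Time 1 as well as Time 2 in 1.3, and relabel the visits in 8.1 as T1 to T4.
2. **Models in 9.3.** Name the mediator wave for each H2 and H5 model. Report the week-4 mediator model with and without the Time 1 mediator, and declare in advance which is primary. State that the adjusted model addresses change after baseline, has lower power, and removes any effect already carried by baseline affect.
3. **Engagement (H5).** Note that total engagement through the week-4 mediator is not time-ordered. Use the Time 1 mediator for total engagement. Use in weeks 5 to 8 given use in weeks 1 to 4 can be an optional sensitivity analysis; the program already logs the dates (6.3). Describe all of these analyses as associational.
4. **If Time 1 has passed without mediators.** Delete the baseline expectation for affect and executive functioning from 9.3, and state that a week-4 indirect effect cannot be separated from a relation present at entry.

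**Cost.** If 8.1 already intends a baseline score, only text changes. Otherwise Time 1 gains about 20 + 12 = 32 items (affect scales plus executive function), against a stated teen burden of 40 minutes. The adjusted model loses power.
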